7. STUDY METHODOLOGY

7.1 Medical history

All clinically significant medical history (including any significant surgical procedures) must be recorded for each subject. Each subjects' full medical history will be obtained through direct questioning and the medical assessment at screening and updated at Day -1. If any clinically relevant observations are made prior to dosing, they will be counted as medical history.

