8. ADVERSE EVENTS

The collection, evaluation and reporting of adverse events/reactions arising from this clinical study will be performed in accordance with:

- Detailed guidance on the collection, verification and presentation of adverse event/reaction reports arising from clinical trials on medicinal products for human use ('CT-3') (2011/C 172/01).
- International Conference on Harmonization (ICH) harmonised tripartite guideline on clinical safety data management: "Definitions and standards for expedited reporting" E2A.
- ICH harmonised tripartite guideline on development safety update report: E2F.
- ICH guideline E2F "Note for guidance on development safety update reports (DSUR)".

It is the investigator's responsibility to document and report all adverse events occurring in the clinical trial. The period of observation for collection of adverse events extends from the signing of the informed consent form up to the final visit. Additionally, spontaneously reported serious adverse events (SAEs) will be collected up until 30 days after the final study visit. SAEs

experienced after this 30-day period will only be reported if the investigator suspects a causal relationship with the study drug.

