8.1 Definitions

An **Adverse Event (AE)** is any unfavourable and unintended sign (including an abnormal laboratory finding), symptom or disease temporally associated with the use of a medicinal product, whether or not considered related to it.

An AE may be:

- A new symptom or medical condition;
- A new diagnosis;
- An inter-current illness or an accident;
- A worsening of a medical condition/diseases existing before the start of the clinical trial;
- The recurrence of a disease;
- An increase in frequency or intensity of episodic diseases;
- A change in a laboratory or other clinical test parameter.
 - The criteria for determining whether an abnormal test result should be reported as an AE/ADR are as follows:
 - The test result is associated with accompanying symptoms, and/or
 - It requires additional diagnostic testing or medical/surgical intervention
- It leads to a change in trial dosing outside of protocol-stipulated dose adjustments, or discontinuation from the trial, significant additional concomitant drug treatment, or other therapy, and/or
- It is considered to be an adverse event by the investigator or sponsor.

An AE does not necessarily include the following:

- An abnormal test that needs repeating, in the absence of any of the above conditions. Any abnormal test result that is determined to be an error does not require reporting as an adverse event.
- Surgical procedures themselves are not AEs; they are therapeutic measures for conditions that require surgery. The condition for which the surgery is required may be an AE/ADR. Planned surgical measures permitted by the clinical trial protocol and the condition(s) leading to these measures are not AEs, if the condition leading to the measure was present before inclusion in the trial and has not worsened. In the latter case, the condition should be reported as medical history.

A **serious adverse event (SAE)** is defined as any adverse event that fulfils any of the following criteria:

- it results in death;
- it is life-threatening (the term "life-threatening" in the definition of "serious" refers to an event in which the subject was at immediate risk of death at the time of the event; it does not refer to an event which hypothetically might have caused death if it was more severe);

- it requires a hospitalisation* or prolongs existing hospitalisation;
- it results in persistent or significant disability/incapacity;
- it is a congenital abnormality/birth defect;

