8.2 Classification

Severity:

The investigator will assess the severity of AEs. All AE/ARs will be graded for severity with guidance from CTCAE v5.0, published 27 Nov 2017.

Changes in the severity of an AE/AR should be documented to allow an assessment of the AE/AR duration at each level of severity.

Application of CTCAE:

Background

CTCAE terminology and grading was developed by the US National Cancer Institute (NCI) to achieve standardised classification of adverse drug reactions in cancer therapy. It is the most comprehensive set of standardised criteria available and is updated regularly. The current version 5.0 was released in November 2017.

The CTCAE displays AE Grades I through V with detailed clinical descriptions of severity for individual conditions and symptoms. The standard grade definitions are described as follows:

Grade I: Mild; asymptomatic or mild symptoms; clinical or diagnostic observations only; intervention not indicated.

Grade II: Moderate; minimal, local or non-invasive intervention indicated; limiting age-appropriate instrumental Activities of Daily Living (ADL)*.

Grade III: Severe or medically significant but not immediately life-threatening; hospitalisation or prolongation of hospitalisation indicated; disabling; limiting self-care ADL**.

Grade IV: Life-threatening consequences; urgent intervention indicated.

Grade V: Death related to AE.

*Instrumental ADL refer to preparing meals, shopping for groceries or clothes, using the telephone, managing money, etc.

**Self-care ADL refer to bathing, dressing and undressing, feeding self, using the toilet, taking medications, and not bedridden.

The NCI CTCAE criteria and their interpretation are consistent with the standard intensity grading for AEs during clinical trials: Grade I: mild, Grade II: moderate, Grade III: severe or medically significant but not immediately life-threatening.

Limitations

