10.3 Statistical analysis of safety

Individual subject demographics (age, gender and race) and body measurement data (height, weight and BMI) at screening will be listed. These demographic characteristics and body measurements will be summarised by treatment group and overall (mean, median, standard deviation, minimum, maximum), using the safety analysis set. Other baseline characteristics will be listed only.

AE, AESI and SAE data will be listed and summarised using descriptive statistics: the number (and %) of subjects who had any AEs and the number of AE episodes will be summarised for each dose. All AEs will be summarised and listed by using system organ class (SOC) and preferred term (PT) assigned to the event using Medical Dictionary for Regulatory Activities

(MedDRA). Furthermore, these events will be summarised by the maximum intensity. The number of subjects who had drug-related AEs will also be summarised. Any AESI, SAEs and/or AEs that led to withdrawal will be summarised and listed.

Vital signs data (SBP, DBP, pulse rate, Respiratory Rate, Temperature) will be listed and summarised, along with changes from baseline, using descriptive statistics (mean, median, standard deviation, minimum, maximum). Out-of-reference-range values will be flagged as high (H) or low (L) and as being clinically relevant or not: the number of subjects presenting out-of-range and clinically relevant values will be summarised.

All safety clinical laboratory data will be listed. Laboratory test results will also be compared to laboratory reference ranges and those values outside of the applicable range will be flagged as high (H) or low (L) and as being clinically relevant or not: the number of subjects presenting out-of-range and clinically relevant values will be summarised. The quantitative laboratory data, along with changes from baseline will be summarised using descriptive statistics (mean, median, standard deviation, minimum, maximum). Change from baseline values at each assessment will be calculated as the assessment value minus the baseline value. The qualitative urinalysis data will be listed only.

Results from the POMs questionnaire will be listed and along with changes from baseline will be summarised using descriptive statistics (n, mean, median, standard deviation, minimum, maximum).

Basic Neurological Examination data will be listed only.

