2.2 Endpoints

Primary

- Safety and tolerability as measured by the incidence of treatment-emergent adverse events (TEAEs) including the clinical signs, nausea, vomiting and diarrhoea, proportion of subjects with clinically relevant changes in laboratory safety tests (haematology, chemistry (in particular ALT, AST and bilirubin increases) and urinalysis), proportion of subjects with morphological and/or rhythm abnormalities on electrocardiogram (ECG), proportion of subjects with clinically significant changes in ECG time intervals (PR, QRS, QT and QTc intervals) and proportion of subjects with clinically significant changes in vital signs (systolic blood pressure, diastolic blood pressure and pulse rate).

Secondary

- PK parameters derived by non-compartmental methods including maximum observed plasma concentration (C_{max}), time to maximum plasma concentration (t_{max}), area under the plasma concentration-time curve from time zero to last detectable plasma concentration (AUC_{0-t}), area under the plasma concentration-time curve from time zero extrapolated to infinity (AUC_{0-inf}), terminal elimination rate constant (λ_z), terminal elimination half-life ($t_{1/2}$).
- Baseline corrected QTc (ΔQTc) as a function of the concentrations of AQ and DEAQ when administered alone, and when administered in combination with ATV-PG.

3. Trial Design

The study is a randomized, double-blind, placebo controlled, parallel group study to determine the tolerability and safety of ATV-PG + AQ, ATV-PG + AQ placebo, ATV-PG placebo + AQ, and ATV-PG placebo + AQ placebo administered once daily for 3 days to healthy adult male and female subjects.

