5.1 Adverse Events

A Treatment Emergent Adverse Event (TEAE) is any adverse event that commences after the start of administration of study drug.

An adverse events of special interest (AESI) is an adverse event of scientific or medical concern specific to the sponsor or the particular product or program, for which ongoing monitoring and rapid communication by the investigator to the sponsor may be appropriate.

The incidence of TEAEs (after dosing) will be summarized using the safety set. The MedDRA dictionary Version 21.0 (or higher) will be used to classify all AEs reported during the study by System Organ Class (SOC) and Preferred Term. A summary of TEAEs including the incidence of subjects who experienced TEAEs (number and percentage of subjects) and incidence of TEAEs (number of events) will be presented for each treatment group and overall, by severity and by relationship to study drug.

Serious TEAEs, AESIs (after dosing) and AEs leading to withdrawal will be summarized by SOC and Preferred Term for each treatment group and overall, and by relationship to study drug.

Subjects having multiple AEs within a category (e.g., overall, SOC and Preferred Term) will be counted once in that category. For severity tables, a subject's most severe event within a category will be counted. For relationship tables, a subject's event with greatest relationship to study drug within a category will be counted. In each table, SOC and Preferred Term will be presented in descending order of overall incidence rate (alphabetical order will be used in case of equal rates).

All adverse events will be listed.

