6.3 Statistical Analysis on PK Parameters

The PK parameters will be listed for each subject and summarized using descriptive statistics (N - the number of subjects, arithmetic mean, SD - standard deviation, CV - coefficient of variation, geometric mean, geometric CV, median, minimum, maximum).

It is noted that for reporting purposes, T_{max} will be described using Median (min, max), and all other parameters will be described using mean, geometric mean and CVs.

7. *Methods for Withdrawals, Missing Data and Outliers*

The individual plasma concentration data and the actual timing of study drug administration and blood sampling will be used throughout the analyses. If there is any doubt about the actual time at which a sample was taken, then the scheduled time will be used. For PK data analysis, please see Section 4.13.1 regarding the handling of missing and BLQ values.

If medication dates are incomplete and it is not clear whether the medication was concomitant, it will be assumed to be concomitant.

AEs with unknown start date/time will be assumed to be treatment-emergent unless the end date/time is known to be before the first administration of study drug. Otherwise missing or partial dates will be listed as such.

There will be no further imputation of missing data (i.e., subjects who prematurely discontinue from the study will not be included in summary statistics or analyses beyond the time of discontinuation).

Depending on the extent of missing values, the appropriateness of the methods described for handling missing data may be reassessed prior to database lock (to examine the sensitivity of results to handling of missing data).

References

- [1] Garnett, C., Bonate, P.L., Dang, Q. et al. Garnett C, Bonate PL, Dang Q, Ferber G, Huang D, Liu J, Mehrotra D, Riley S, Sager P, Tornoe C, Wang Y. Correction to: Scientific white paper on concentration-QTc modelling. *J Pharmacokinet Pharmacodyn.* 2018b; 45 (3): 399.

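### The SAP defines a treatment-emergent AE by onset only, so a symptom that worsens after dosing is counted or not depending on how it was recorded before dosing

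*SAP*

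**What the plan says.** The primary endpoint in SAP 2.2, identical in Protocol 2.2.1, opens with "Safety and tolerability as measured by the incidence of treatment-emergent adverse events (TEAEs) including the clinical signs, nausea, vomiting and diarrhoea". The protocol uses the term TEAE but does not define it. The definition is in SAP 5.1: "A Treatment Emergent Adverse Event (TEAE) is any adverse event that commences after the start of administration of study drug". SAP section 7 adds only a rule for missing dates: "AEs with unknown start date/time will be assumed to be treatment-emergent unless the end date/time is known to be before the first administration".

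Four protocol statements bear on events seen before dosing:

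- Section 8, on when AEs are collected: "The period of observation for collection of adverse events extends from the signing of the informed consent form up to the final visit". Table 1 accordingly schedules AE recording at screening and on Day -1.
- Section 8.2, on severity: "Changes in the severity of an AE/AR should be documented to allow an assessment of the AE/AR duration at each level of severity".
- Section 7.1, on medical history: "If any clinically relevant observations are made prior to dosing, they will be counted as medical history".
- Section 8.1, which lists among the things that may be an AE "A worsening of a medical condition/diseases existing before the start of the clinical trial".

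For the analysis, Protocol 10.3 plans that "the number (and %) of subjects who had any AEs and the number of AE episodes will be summarised for each dose", with further summaries by maximum intensity and drug-relatedness and no restriction to TEAEs. SAP 5.1 builds its incidence, severity and relationship summaries on TEAEs, and lists all AEs.

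**The concern.** A TEAE definition usually has two limbs: onset after first dose, and worsening after first dose of something already present. SAP 5.1 has only the first. That would matter little if the protocol ensured that every post-dose worsening became a new AE with its own start date, but it does not say so. Whether a worsened symptom reaches the primary tables then depends on recording practice and not on what happened to the subject.

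Tolerability is the purpose of the study, so the symptom counts carry weight. Protocol 1.2.2.1 calls weakness, headache, dizziness, nausea, vomiting and diarrhoea very common with amodiaquine. Some of these could plausibly be present before dosing. Headache is an example, since Table 5 has subjects stop caffeine 48 hours beforehand.

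The SAP handles the same straddling problem elsewhere. Section 4.10 states how to class a medication that spans the first dose, and section 5.2 tabulates shifts from baseline grade to worst post-dose grade for laboratory values. Symptom AEs have no equivalent.

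**Working it through.** **Step 1. Can pre-dose AEs be in the data?** Yes. Protocol 8 and Table 1 collect them from consent. The missing-date rule in SAP section 7 also allows for an AE that ended before the first dose.

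**Step 2. Follow one event down each recording route.** Take a hypothetical subject with a mild headache on Day -1 that becomes moderate after the first dose.

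| | Recorded as a pre-dose AE | Recorded as medical history |
|---|---|---|
| Basis for the pre-dose entry | Protocol 8, Table 1 | Protocol 7.1 |
| Basis for the worsening | Protocol 8.2: severity change documented for that AE | Protocol 8.1: worsening of an existing condition is itself an AE |
| Start date of the AE | Day -1 | Day 1, after dosing |
| TEAE under SAP 5.1? | No | Yes |
| In TEAE incidence, severity and relationship tables? | No | Yes |

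Two links in this table are inferences. In the left column, Protocol 8.2 does not state that the original onset date is kept, but it gives no instruction to open a new record, and Protocol 8.3 asks for one onset date per event. In the right column, the 8.1 wording concerns conditions that existed before the trial began, so applying it to something that arose between consent and dosing is a reading of the text.

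The missing-date rule makes the gap easier to see. The same headache with an unknown start date, still present after dosing, would be assumed treatment-emergent. With its Day -1 start correctly recorded, it would not be.

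**Step 3. Which components are exposed?** Laboratory values have CTCAE shift tables and changes from baseline (SAP 5.2). ECG intervals (SAP 5.3) and vital signs (SAP 5.6) are summarised as change from baseline. None of these uses the TEAE flag. The exposure is therefore confined to symptom-type AEs in the TEAE tables.

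**Step 4. Weight of one subject.** The plan states no figure to reproduce, because the sample size has no formal basis (SAP 3.3). Arm sizes from SAP 3.1 are 8 in Treatment 1 and a planned 12 in each of Treatments 2, 3 and 4, so 8 + 12 + 12 + 12 = 44. If *k* subjects in an arm of size *n* have a worsened pre-dose AE as their only qualifying event, incidence changes by *k*/*n*:

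| *k* | Treatment 1 (*n* = 8) | Treatments 2, 3, 4 (*n* = 12 each) |
|---|---|---|
| 0 | 0 | 0 |
| 1 | 1/8 = 12.5 points | 1/12 = 8.3 points |
| 2 | 2/8 = 25.0 points | 2/12 = 16.7 points |

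The documents give no value for *k*. SAP 5.1 counts a subject once per category, so the condition on a single qualifying event is essential. For overall incidence, the subject must have no other TEAE. For a preferred-term row, the subject must have no other TEAE coded to that term, which is easier to meet.

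**The case against.** The strongest reply is that Protocol 7.1 is the one rule that says how a clinically relevant pre-dose observation is classified, namely as medical history. A later worsening then starts after dosing and satisfies SAP 5.1 as written. On that view the conflict lies between Protocol 7.1 and section 8, and it may be settled in the study operations manual, to which section 8.2 defers further detail and which is not available here. This stands in part. A reader might infer that the SAP always drops a worsened pre-dose event, and the documents do not support that: the loss depends on the recording route. Equally, 7.1 does not count the event by itself; the count comes from 8.1. But Table 1 still schedules AE recording before dosing, and neither document says which route prevails.

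A second reply is that such events do not vanish. All AEs are listed, AEs leading to withdrawal are tabulated without restriction to TEAEs, and the adverse reaction rules in Protocol 4.4 would bring a severe reaction to notice at once. All true, and it limits the harm. A listing does not, however, restore a missing count in the primary tables.

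A third reply is that the study is exploratory and descriptive, with no test or threshold resting on TEAE incidence. That also stands, and it keeps the matter to one of accurate description.

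**Conclusion.** The concern holds in conditional form. The same post-dose worsening is excluded from the TEAE incidence, severity and relationship tables, or included in them, according to whether the pre-dose symptom was entered as an AE or as medical history, and the plan does not choose. The effect is 8.3 or 12.5 percentage points for each subject whose only qualifying event, overall or within a preferred term, is such a worsening. The number of such subjects is unknown and may be zero.

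Two stronger conclusions should not be drawn. A reader might infer that a particular number of subjects is lost from the primary count. The documents give no rate of pre-dose AEs or of their worsening, and a subject with any other TEAE remains in overall incidence. A reader might also infer a downward bias against the active arms. Pre-dose complaints arise before treatment in every arm, and one such as headache after stopping caffeine could worsen on placebo too. A drug effect would make worsening likelier on active treatment, but that is an expectation and not something the documents show.

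**What to change.** 1. In SAP 5.1, define a TEAE as any AE that starts, or increases in severity, after the first dose. In the severity tables, use the maximum post-dose grade.
2. Reconcile Protocol 7.1 with sections 8 to 8.2, so that a pre-dose event is recorded one way for all subjects. This should cover those already dosed when Treatment 1 was stopped (20 at that point); otherwise the data set will mix two conventions.
3. State that each worsening is counted once, either as a grade increase on the existing record or as a new record with its own start date, not both. SAP 5.1 also reports numbers of events, so using both would inflate those counts even though each subject is counted once per category.
4. Settle all this before unblinding.

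The cost is a sentence or two in the SAP, a protocol clarification with a CRF completion note, and a check of the pre-dose AE and medical history entries already made. If the existing-record route is chosen, it relies on dates of grade change being retrievable. Protocol 8.2 implies that they are, but the items listed in 8.3 do not name them. The downside is that TEAE counts may rise slightly in any arm, including placebo.

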5.2 Laboratory Data

Clinical laboratory parameters (including blood chemistry, hematology, coagulation, urinalysis and other laboratory results) will be listed and abnormal parameters will be flagged as high (H) or low (L) according to reference ranges. Absolute (observed) values and changes from baseline (continuous variables) will be summarized for each parameter and scheduled time point by treatment group. The last lab value will be used for summary analysis if repeated measurements are made at any time point.

For summary statistics, a lab value with "<" will be replaced with a numeric value by removing the "<" sign. In the listings, the values will be displayed as originally reported by the laboratory.

Laboratory parameter values will be graded according to the Common Terminology Criteria for Adverse Events. Shift tables by treatment group will be produced for these laboratory parameters. These tables will summarize the number of subjects with each baseline grade relative to the normal ranges and changes to the worst highest grade assessed post-dose during the study.

The qualitative urinalysis data will be listed only.

